Each participant will meet with [name] to go over the possible side effects of 30 mg of Morphine, 50 mg of Naltrexone and placebo given at one dose. [name] will go over the most common side effects and will emphasize the risk of altered mental status (e.g. sleepiness, drowsiness) after one dose of morphine. [name] is Yale trained psychiatrist and will collect psychiatric history on possible previous misuse of alcohol, illegal drugs and prescription drugs. Any subject with such previous history will be excluded from the study. In addition, each participant will be given a patient information sheet about each of the medications used in the study.

To avoid fatigue subjects will take a 5-minute breaks every 15-20 minutes. This session takes about 2 hours. If the subject meets all eligibility criteria we will schedule them for a Presupplementation session at The John B Pierce Laboratory.

Measurment of body fat composition:

We will measure body fat composition of our participants; body fat and body mass index can be confounding in our analysis given that brain response to food is different between obese and healthy weight participants³⁶. The BodPod body composition tracking system is an air displacement plethysmograph which uses whole-body densitometry to determine body composition (fat and fat-free mass). The BodPod is an egg-shaped pod that consists out of two chambers. The front, or Test chamber, is where the subject sits and is comprised of a seat that forms a common wall separating it from the rear, or reference chamber. During the brief data collection period of the volume measurement, the chamber door is secured by a series of electromagnets and a gasket. A diaphragm is mounted on the common wall, which oscillates during testing. This causes small changes in volume inside the chamber, of which the pressure response to these small volume changes is measured. This is done by measuring the interior volume of the empty BodPod chamber, then measuring it again when the subject is seated inside. By subtraction, the subject's body volume is obtained. Once the subject's mass and volume are determined, body density is calculated and the relative proportions of fat and fat-free mass are determined. Thus this procedure is entirely non-invasive. A complete test requires about 5

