- Upon arrival to the Magnetic Resonance Research Center (MRRC) participants a urine drug test will be obtained as well as Breath alcohol levels will be assessed with the Alcohawk Elite Breathalyzer. If any of these tests are positive the study will be cancelled. Next, vitals signs (VS)(blood pressure, heart rate, respiratory rate, pulse oximetry, and temperature). If the urine drug test is positive for opiates or methadone the study will be cancelled and the subject disqualified for this study.
- Participants with BP < 90/60 and/or heart rate < 60 will be excluded and the study will be cancelled. VS will be logged in to a VS sheet and kept with the participant paper record in our study binders. Mental and neurologic status will be assessed for a baseline using the National Institutes of Health (NIH) Stroke Scale Neurological Assessment flow sheet (see attached form).
- 3. Next 20 ml of blood will be withdrawn. All blood samples will be placed in pre-chilled test tubes, and centrifuged at 4 C and the plasma stored at -70 C until analyzed according to standard procedures in the YCCI Core Laboratory
- 4. Next, participants will be undergo fMRI scanning: fMRI session: Set up is as above for fMRI simulator in fMRI training. Prior to getting the subject into the MR-room all people involved with the study walk through a detector designed to detect metal objects. We will use a Siemens 3T Trio TIM scanner with a 32channel head-coil. A T1-weighted 3D MPRAGE sequence (4 minutes) will be performed to obtain a high-resolution anatomical image and echoplanar imaging will be used to measure

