the BOLD signal as an indication of cerebral activation in response to various tastes (milkshake and tasteless) during two 9.6-minute runs and in response to sucrose and tasteless during two 9.6-minute runs. A run consists of multiple blocks of taste (milkshake or tasteless). One block is a series of 4 - 8 presentations of tastes or tasteless; Each presentation starts with a 0.75 cc delivery of liquid over 2 s followed by 7 s in which to swallow. Each taste block is followed by a rinse (0.75 cc deionized water). Before the start of a new block there is a rest period of 10 seconds. Blocks vary in length between 32 and 80 seconds and the order of blocks is counterbalanced across subjects. This design is modified from prior event-related designs so as to yield a 61% improvement in design efficiency (calculated by FMRIB's software library FSL), which we confirmed to lead to more extensive and more intense BOLD response. The data can be analyzed offline and used for experimental control variables. Next, two 6 minutes resting state runs will be collected. During these runs, participants will be asked to stare at a cross-hair on the screen. Finally, a diffusion tensor imaging (DTI) scan will be obtained over 5 minutes.

5. Participants will be then taken out of the scanner and given one oral dose of either 30 mg of Morphine, or 50 mg of Naltrexone or placebo. 60 minutes later, VS will be collected again and logged in to the VS sheet and participants will undergo another scanning session while receiving milkshake, sucrose or tasteless solutions as described in 3 and while at rest. DTI and structural imaging will not be repeated. Blood pressure and heart rate will be continuously monitored during scanning using the Biopac system. The same procedure will be followed for the same participants in two subsequent visits (Day 4 and Day 5). *The*

Figure 1. Schematic illustration of study design; the order is just one example for one participants; the interventions will be randomized in a double blind protocol.

visits will be scheduled within a period spanning 4 weeks but no two-treatment days will be scheduled less than 48 hours apart. The overall design of the study will follow the illustration in Figure 1. However, the order of the interventions (i.e. Morphine, Naltrexone or placebo) will be randomized. The scanning session after medication administration will last between 45-60 minutes. Participants vital signs and mental

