and neurological state will be monitored for an additional 2 hours post-scanning at an interval of one hour using the NIH Stroke Scale Neurological Assessment flow sheet (two assessments in total); after 2 hours, if participants mental and neurologic state and VS are stable they will be reminded about side-effects of morphine and naltrexone and released. Morphine sulfate half-life is 2-4 hours. By the time our participants leave the MRRC one to two half-lives would have passed and the blood level of morphine would have dropped 2 to 4 times relative to time at ingestion.

B. Description of the open label arm

The same procedures described in A will be used to study 15 CBP patients using an open label design except when participants are taken to the scanner. At that point both the experimenter and the participant will know that morphine 30 mg is being administered. In addition, this arm of the study will have one arm only.

4. Genetic Testing N/A

A. Describe

i. the types of future research to be conducted using the materials, specifying if immortalization of cell lines, whole exome or genome sequencing, genome wide association studies, or animal studies are planned.

No future research is planned with the materials. We will determine the presence or absence of candidate opiate activity-related genes after the subject has provided their saliva.

ii. the plan for the collection of material or the conditions under which material will be received

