Eligibility will be determined by the research coordinator upon initial telephone contact using a screening form (see attached phone screening form). The form asks general information questions (date of birth, handedness, native language, etc.) and queries the participants about their health and any history of conditions known to affect cognitive functioning (e.g. stroke, medications, head trauma), or any conditions that could compromise the safety of conducting an MRI scan (e.g. claustrophobia, metal in the body, pacemaker). A more lengthy MRI safety screening form will be administered when the participant arrives for the scanning session (see attached MRI screening form) at the Magnetic Resonance Research Center in the Congress Avenue building of Yale School of Medicine. We do not wish to study females who are or may be pregnant. Therefore, as part of our MRI safety screening protocol, all females of childbearing potential will be given a urine pregnancy test prior to scanning. Results of the pregnancy test will be given to them only and will remain confidential. If the results indicate a subject is pregnant she will not participate in the fMRI scan, and will be excluded from the study.

9. **Risks:** Describe the reasonably foreseeable risks, including risks to subject privacy, discomforts, or inconveniences associated with subjects participating in the research.

Risk involved with the questionnaires

It is possible that interviews may cause distress or concern to the participants. One potential risk to participants is that it may be distressing to disclose information about psychiatric difficulties such as previous history of substance misuse. In our estimation, there is a low risk of this possibility and the effects would probably be short lived. We have conducted several hundred of these interviews with no adverse effects. It is possible that subjects may become frustrated with some of the impulsivity or cognitive assessments. We have conducted hundreds of similar cognitive assessments and have had no adverse outcomes.

Risks involved with the mock fMRI scanner

Page 21 of 52

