Minimizing risk involved with administration of one oral dose of Morphine and Naltrexone

We will minimize the acute risk of administration of oral 30 mg Morphine or 50 mg of Naltrexone by carefully monitoring vital signs and mental status using neuro-checks every 60 minutes after the administration. In addition, the study physician [name] will always be present during the whole duration of the visit when either of these drugs is administered.

Minimizing risk involved with the questionnaires:

Should a subject meet diagnostic criteria for any psychiatric disorder [name] will refer them for treatment. If a participant appears to be distressed or fatigued during assessments, the assessor will halt the procedure and take a break. The session will only recommence when and if the participant reports feeling capable of continuing

Minimizing risks involved with the mock fMRI scanner

We will attempt to minimize any discomfort associated with the mock fMRI scanner by informing the subject about what to expect prior to participation and explaining to them the equipment, how it works, which parts are replaced for every subject and how we clean any components that are not. Subjects will be instructed to tell the experimenter if they feel any discomfort with the procedure so that the session can be terminated.

Minimizing risks involved with MRI

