During the fMRI scans, the participants will be monitored for anxiety or related concerns by research personnel associated with the project. Participants and investigators will be screened for metallic objects prior to entering the scan room. Prior to inclusion in the study, the presence of potential MRI risks, such as pacemakers, surgical clips, or metallic devices will be excluded by medical and surgical history administered during screening. All subjects will wear foam earplugs and sound-reducing headphones to reduce risk of hearing damage due to the loud noise of the scanner. The minor risk of discomfort due to lying still for 60 minutes will be minimized by providing custom pads and pillows designed to make the participants as comfortable as possible. Participants will communicate with the MR technologist and research assistant via an intercom system and may trigger and audible alarm at any time to stop the MRI session if he or she is uncomfortable or anxious. In addition, all imaging center staff, students, post-docs and research assistants will participate in safety training annually. Finally, all subjects are familiarized with MR procedures during the training session in the mock scanner to ensure that subjects that are schedule for the MR scan are comfortable with the procedures.

Minimizing risks related to pregnancy

To minimize risks related to pregnancy, we inform the subject that if they should become pregnant, they should report this to their health care professional, physician and to us immediately. If this happens during the study, the subject will stop his/her participation. We perform pregnancy tests along with toxicology tests during each assessment and intake.

Minimizing risks associated with the BodPod

The experimenter can see the subject at all times in the BodPod and will show them the alarm button inside the BodPod that will interrupt the measurement if they feel anxious.

Minimizing risks for toxicology screenings:

Every subject will use a new separately wrapped mouthpiece that will be attached to the breathalyzer. Bottles containing subject's urine specimens will be not be labeled and will be appropriately discarded in a biohazard container after instant testing. This information is not recorded.

Minimizing risks for saliva sample collection and genotyping:

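### In the visible text, no scheduled step asks about symptoms after release at about 4 hours post-dose, so the per-subject adverse-event review has no systematic data on later effects

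*Combined protocol and SAP*

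**What the plan says.** Section V, item 3.A (Day 3) sets out the dosing visit. Vital signs are taken 60 minutes after the oral dose. A scan of 45 to 60 minutes follows, with continuous blood pressure and heart rate. Two hourly checks of vital signs and the NIH Stroke Scale then fill a further 2 hours. The visit ends this way: "if participants mental and neurologic state and VS are stable they will be reminded about side-effects of morphine and naltrexone and released". Item 10 summarises the drug safeguard as "carefully monitoring vital signs and mental status using neuro-checks every 60 minutes after the administration".

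For the later crossover visits the rule is "The same procedure will be followed for the same participants in two subsequent visits (Day 4 and Day 5". Arrival consists of urine drug and breath alcohol tests, vital signs and a blood draw, and "Mental and neurologic status will be assessed for a baseline". Item 8 adds that "A more lengthy MRI safety screening form will be administered when the participant arrives for the scanning session". Item 10 adds "We perform pregnancy tests along with toxicology tests during each assessment and intake".

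Item 3.B applies the same procedures to 15 open-label patients, who know that they receive morphine 30 mg. The payment table in Section X, item 2 lists two fMRI sessions for that arm.

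The safety plan (Section V, item 11) commits to monitoring adverse events in every subject but names no method of asking and no collection window. The principal investigator reviews each subject's events at completion, weighs their frequency and severity, and decides whether the protocol or consent form needs changing. A safety review also takes place at least every 6 months.

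Other safeguards are described. The study physician "will always be present during the whole duration of the visit when either of these drugs is administered", and at intake "each participant will be given a patient information sheet about each of the medications used in the study".

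**The concern.** The per-subject review is meant to judge how often adverse events occur and how severe they are. That needs events to be collected in the same way from everyone over a defined period. As described, the active checks look at vital signs and neurologic or mental status, and they stop at release.

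Some effects that Section V, item 9 itself lists as acute would rarely show in a stay of about 4 hours. Insomnia after naltrexone and constipation after morphine are the clear examples. Nothing in the visible text prompts a participant to mention these at the next visit, and after the last crossover dose there is no described visit or call at all. The protocol rates the study as moderate risk and does not regard either drug as minimal risk, so some structured look beyond the first 4 hours would be expected.

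At stake is whether the review can detect that late effects are more frequent or more severe than the consent form suggests.

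**Working it through.** **Observation time per dose** (item 3.A): 60 min to the post-dose check + scan of 45 to 60 min + 120 min = 225 to 240 min = 3.75 to 4.0 h. This is nominal. It assumes that the scan starts straight after the 60-minute check, and an unstable participant would stay longer.

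**The plan's own figure.** Item 3.A gives a morphine half-life of 2 to 4 h and says one to two half-lives have passed at release, with a 2- to 4-fold fall in level. Half-lives elapsed = release time / half-life: 3.75/4 = 0.94 up to 4.0/2 = 2.0. Fold fall = 2^(half-lives): 2^0.94 = 1.92 up to 2^2 = 4.0. The figure reproduces apart from rounding. On the protocol's simplification (decay from ingestion), 25% to 52% of the level remains at release.

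**Time to the next described contact.** Treatment days are at least 48 h apart, so after a non-final dose the earliest is 48 − 4.0 = 44 h to 48 − 3.75 = 44.25 h after release. After the final crossover dose, none is described.

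**Number of doses.** Inputs: target 75 (Section VII, item 1); 15 open-label patients with one dose each (Section V, item 3.B; Section VI, A.2); three doses per crossover participant. Assume that the 75 include the 15 and that all complete.
- Crossover participants: 75 − 15 = 60.
- Total doses, placebo included: 60 × 3 + 15 × 1 = 195.
- Doses followed by a later crossover visit: 60 × 2 = 120.
- Final doses with no described later contact, if the second paid open-label session follows the dose: 60, and 60/195 = 31%.
- The same, if it does not: 60 + 15 = 75, and 75/195 = 38%.

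**Active drug among those final doses.** The protocol says only that order is randomized. If it is balanced, two thirds of crossover final doses are active: 60 × 2/3 = 40. Adding the 15 open-label morphine doses where they count gives 40 + 15 = 55. The range is 40 to 55.

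**If the 15 are additional to the 75.** Total doses are 75 × 3 + 15 = 240. Final doses without described contact are 75 to 90, and 75/240 = 31% to 90/240 = 38%. The share barely moves.

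**Events missed.** This cannot be computed. Section VI, A.2 lists insomnia with naltrexone at 3% to 14% and constipation with morphine at 9% to >10%. It does not present these as single-dose rates, and it says the naltrexone rates above 10% combine oral and injectable forms.

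**The case against.** The strongest reply is that this reads too much into silence. The plan does promise monitoring for each subject, a review at completion and a review at least every 6 months. The medication information sheets, attached forms and consent pages are not visible and could tell participants to report later effects. This stands. A reader might infer that late effects are recorded only if the participant volunteers them, but the documents do not say so. What can be said is that no scheduled question is described.

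A reader might also infer that every participant's last dose goes without later contact. The two paid open-label sessions prevent a firm count of 75. They may be two visits, with the second after the dose, and the text does not settle this. About a third of crossover final doses would also be placebo under balanced order.

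The consequence is limited too. These are single doses of marketed drugs, a physician is present throughout drug visits, release depends on stability, and participants are briefed and reminded. Each drug is given once, so a poorly tolerated one is not repeated, and the 120 non-final crossover doses are followed by a visit with vital signs and a neurologic check. The named late effects are already disclosed and would not normally meet the protocol's three-part test for reporting to the IRB. All of this holds and keeps the point minor. It does not give the completion review any structured information on what happened after release.

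**Conclusion.** The point holds as a modest gap in safety ascertainment, worth considering. Following the visible schedule, nobody asks about symptoms after about 3.75 to 4.0 hours. For 60 to 75 of 195 doses (31% to 38%), of which about 40 to 55 are active drug, no later contact is described. The counts assume that the 75 include the 15 open-label patients, that all complete and, for the active-drug figure, that order is balanced. The range reflects the unclear timing of the second open-label session.

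The documents do not support a claim that serious events would be missed, or any estimate of how many events go unrecorded. The fMRI endpoints and their analysis are unaffected. If an unseen form or sheet already asks about later symptoms, citing it with its timing would close that part of the point.

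**What to change.** Keep the existing monitoring and reviews, and add two steps.

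1. At arrival on Day 4 and Day 5, before dosing, ask a scripted adverse-event question with one symptom list whatever drug was given, so that the blind is kept. The physician already on site sees the answers before the dose.
2. The coordinator who already does the telephone screening makes one scripted call the day after the last dose, in both arms, before the per-subject review. State whether the second open-label session follows the dose; if it does, the question could be asked there instead.

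Cost: 60 to 75 calls at an assumed 5 minutes each, or 60 × 5/60 = 5 h to 75 × 5/60 = 6.25 h of staff time, plus a short form. Recorded adverse-event rates will be somewhat higher because participants are now asked.

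### Release after dosing is timed from the end of the post-dose scan, with no minimum time from the dose, so a scan that is cut short or never started shortens the stay or leaves it undefined

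*Combined protocol and SAP*

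**What the plan says.** The rule is in Section V, item 3 (Research Plan), part A, under the Day 3 fMRI scan session. A participant is scanned, takes a single oral dose of morphine 30 mg, naltrexone 50 mg or placebo, and 60 minutes later has vital signs taken and is scanned again. On length, "The scanning session after medication administration will last between 45-60 minutes". Observation afterwards covers vital signs and mental state, "and neurological state will be monitored for an additional 2 hours post-scanning at an interval of one hour". The checks are made "using the NIH Stroke Scale Neurological Assessment flow sheet (two assessments in total". Release follows "after 2 hours, if participants mental and neurologic state and VS are stable". The protocol gives a morphine half-life of 2 to 4 hours and supports the timing with two statements. The first is "By the time our participants leave the MRRC one to two half-lives would have passed". The second concerns concentration: "the blood level of morphine would have dropped 2 to 4 times relative to time at ingestion".

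Part B applies the same procedures to the open label arm.

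Section V, item 10 (Minimizing Risks) requires neurological checks every 60 minutes counted from administration and keeps the study physician present for the whole visit. It states no release time. Section V, items 9 and 10, allow a participant to stop the scan or leave the study at any point.

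**The concern.** Drug elimination runs from the dose, but the release clock runs from the end of the scan. After the same dose, the person with the shortest post-dose scan may therefore leave soonest. Someone who is dosed but does not go back into the scanner has no scan end from which to count.

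What is at stake is the safety of release. Participants may not be taking opioid analgesics, and a urine test positive for opiates disqualifies them. Section VI, A.2 shows that 30 mg is the top of the usual starting range of 10 to 30 mg. The monitoring plan in Section V, item 11 does not class the morphine risk as minimal. The half-life sentence is the only pharmacological support offered for the release time, so it is worth knowing when the schedule delivers it.

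Separately, a fall in blood level measured from the moment of swallowing has no clear meaning for an oral dose, because there is no blood level at that moment to fall from.

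**Working it through.** **Inputs (Section V, item 3, Day 3)**
- Dose to start of post-dose scan: 60 min.
- Post-dose scan: 45 to 60 min as stated.
- Observation after the scan: 120 min.
- Half-life: 2 to 4 h.
- Listed runs: milkshake and tasteless "during two 9.6-minute runs and in response to sucrose and tasteless during two 9.6-minute runs", then "two 6 minutes resting state runs will be collected". Structural and diffusion imaging are not repeated after the dose, so the listed post-dose runs take 4 × 9.6 + 2 × 6 = 50.4 min.

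**Formulae**
- Time from dose to release: T = 60 + scan length + 120 min.
- Half-lives elapsed: T divided by the half-life, using 240 min and 120 min for the two ends of the range.
- Extra stay under a 4-hour floor: 240 − T.

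**The protocol's own figure.** With a 60-minute scan, T = 60 + 60 + 120 = 240 min. Then 240/240 = 1.00 and 240/120 = 2.00 half-lives, and 2^1 = 2 and 2^2 = 4 give the stated 2- to 4-fold fall. Both figures reproduce exactly, so the sentence counts from dosing with the longest planned scan.

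**Other scan lengths**

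| Post-dose scan | T (min) | T (h) | Half-lives at 4 h | Half-lives at 2 h | Extra stay with 4 h floor (min) |
|---|---|---|---|---|---|
| 60 min | 240 | 4.00 | 1.00 | 2.00 | 0 |
| 50.4 min (listed runs) | 230.4 | 3.84 | 0.96 | 1.92 | 9.6 |
| 45 min | 225 | 3.75 | 0.94 | 1.88 | 15 |
| Stopped at once | 180 | 3.00 | 0.75 | 1.50 | 60 |
| Dosed, not scanned | undefined | undefined | undefined | undefined | undefined |

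The row for a scan stopped at once is a lower bound. It assumes that the scan starts exactly 60 min after the dose and that the two-hour observation begins when the participant leaves the scanner. Any scan stopped part-way falls between that row and the planned-length rows.

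**Untimed steps.** The protocol gives no duration for vital signs, metal screening or fitting the taste-delivery equipment. Where these add to the scan length, T rises by the same amount. For the 50.4 min of listed runs, 9.6 min of such steps brings T to 240 min; for a 45-minute session, 15 min does.

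**Is there a floor elsewhere?** The hourly checks in Section V, item 10 are counted from the dose but have no end point, so they do not supply one.

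**The case against.** The strongest objection is that the half-life sentence is commentary. The operative rule is clinical stability after two hours, with dose-anchored hourly checks and a physician present throughout. Nothing in the documents makes one half-life a safety threshold, or shows that 4.0 h is safer than 3.84 h in someone who is stable. This stands, and it limits the weight of the point. It does not supply a release time for a participant who is dosed but not scanned.

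Two stronger readings are tempting, and the documents support neither.

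- A reader might infer that the half-life statement is true only for a 60-minute scan. That requires no untimed minutes between dose and release, which the documents do not establish. A 45-minute session also could not hold all 50.4 min of listed runs. A value of 0.94 to 1.00 at the extreme 4-hour half-life is fairly described, in rounded terms, as about one.
- A reader might take the 15-minute cut-off in the payment note (Section X, item 2) as evidence that early stopping of the post-dose scan is expected. In the randomised study, payment is for three fMRI sessions, which fits one per visit. Each visit opens with a pre-dose scan whose listed components total 4 + 38.4 + 12 + 5 = 59.4 min. On that reading, anyone who has been dosed is already past 15 minutes. The open label table lists two sessions and is less clear, but it does not point to the post-dose scan either.

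It is also fair to say that mock-scanner training and the long pre-dose scan will remove many people who cannot tolerate scanning before they receive any drug, and that a floor can only be advice to someone who withdraws. Both points reduce how often the change would bind. Neither removes the gap for a participant who stays enrolled after an early stop, or who is dosed and not scanned.

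**Conclusion.** The point holds as a gap in the release rule. For planned-length scans, release comes at about 3.75 to 4.0 h after dosing or slightly later, and the protocol's description is approximately right; the shortfall is at most 15 min and set-up time may close it. For a post-dose scan stopped early, release could be as early as about 3 h after dosing, or 0.75 of a 4-hour half-life, on the two assumptions stated with the table. For a participant dosed but not scanned, the release time is not defined. The documents give no rate for these cases, so no number of participants can be claimed, and they do not support a conclusion that release under the present rule is unsafe.

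The statement about the fall in blood level from ingestion should go whatever the scan length. No endpoint, estimate or error rate is affected. The change is optional and cheap.

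**What to change.** In the Day 3 text, replace the release rule with wording such as: *Release is at the later of 2 hours after leaving the scanner and 4 hours after dosing, whether or not the post-dose scan is started or completed. Hourly vital-sign and neurological checks (at least two assessments) continue until then, with a final check at release, and the stability criterion must still be met. Anyone who withdraws is advised to stay for the same period.* Apply it to all three blinded treatments and to the open label arm.

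Four hours is the upper end of the protocol's own half-life range. Reword the justification to say that *at least one morphine half-life (2-4 hours) has elapsed since dosing*, and delete the sentence on the 2- to 4-fold fall from ingestion.

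**Cost.** Protocol wording, and consent wording if it states visit length. The extra stay is 0 to 15 min after a planned-length scan and up to 60 min after an early stop, with one further check for anyone whose stay is extended. The study physician is already there for the whole visit.
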